Supporting analyses include other measures of diabetic nephropathy and neuropathy and sensitivity analyses accounting for competing risk of death.

Supporting outcomes related to diabetic nephropathy will be derived from serum creatinine. Serum creatinine was collected annually from baseline to year 4 and biannually thereafter in LA and LA-C. **Estimated Glomerular filtration rate (eGFR)** will be calculated based on CKD-Epi equation [Levey, 2009]. Renal outcomes for supporting analyses will be the **doubling of serum creatinine from baseline** and **serum creatinine ≥ 2.5 mg/dl**. These will be analyzed as time until first occurrence of an event. Because death censors the occurrence of renal events, we will conduct a sensitivity analysis to examine these renal outcomes (including ESRD) accounting for the competing risk of death. We will create an indicator variable to distinguish between three different states: participants who experienced a particular renal event, participants who died before experiencing a particular renal event, and participants who were censored at their last available follow-up visit. We will fit a Cox model to estimate type-specific hazard ratio treating the participants who died without experiencing a particular event as censored. Alternatively, we will model the cumulative incidence function and estimate the subdistribution hazard ratio. The cumulative incidence function will be plotted for DSE and ILI.

We will also compare the average level of eGFR over time between DSE and ILI using linear mixed effects models. The basic model will include an indicator variable for intervention assignment, follow-up time, and the interaction between the intervention and follow-up time while adjusting for clinic centers and baseline eGFR. Least square means will be plotted to portray the trend over time. The average post-randomization levels of the overall eGFR for DSE and ILI will be estimated and compared using linear contrasts. The difference in average score between DSE and ILI at a particular visit will also be compared using linear contrasts. The covariance between repeated measures will first be characterized with an unstructured

covariance structure. If the model does not converge, we will explore simpler covariance structures such as compound symmetry. Akaike information criterion (AIC) will be used to aid in selection of an appropriate covariance structure.

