Diabetic neuropathy will be measured by **Michigan Neuropathy Screening Instrument (MNSI)**. It includes two separate assessments: a 15-item questionnaire and a lower extremity examination. The **MNSI questionnaire score** will be the sum of fifteen items (with items 7 and 13 reverse coded) and range from 0 to 15. The score will be dichotomized with ≥ 4 being abnormal [Herman, 2012]. MNSI questionnaire was administered in LA annually and in LA-C and will be collected at the two clinical visits in LA-E. All data collected since randomization will be included. The presence of $MNSI \geq 4$ will be analyzed using logistic regression models appropriate for repeated binary outcomes. The model will use GEE, a logit link, and a binomial variance. Given the large number of repeated measures, we will use an exchangeable correlation matrix and a robust covariance estimate. The basic model will include baseline presence of $MNSI \geq 4$, an indicator variable for intervention assignment, follow-up time, and the interaction between the intervention and follow-up time while adjusting for clinic centers. Significance for the intervention effect will be based on the likelihood ratio test. Overall odds ratio and 95% confidence intervals will be constructed from the fitted models. The difference in average proportion of participants with $MNSI \geq 4$ between DSE and ILI at a particular visit will be compared using linear contrasts.

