The clinical exam component of the MNSI was added in LA-C and will be repeated at the two clinical visits in LA-E, leading to a maximum of three measurements on the MNSI exams for an individual. The **MNSI exam score** will be the sum of eight items (four on each foot) that inspect abnormality in appearance, ulcer, ankle reflexes, and vibration sensation. The score will range from 0 to 8, with higher scores indicating potential neuropathy. Additionally, we will incorporate a participant's **amputation** history into deriving the MNSI exam scores. We will use linear mixed effects models to test the intervention effect. The basic model will include an indicator variable for intervention assignment, follow-up time, and the interaction between the intervention and follow-up time while adjusting for clinic centers. The covariance between repeated measures will be characterized with an unstructured covariance structure. We will also assess the intervention effect on prevalence of MNSI exam score of ≥ 2.5 [Feldman, 1994] using generalized estimating equations. In LA-C (once) and again in LA-E (twice), we will perform the **monofilament test** to examine touch sensitivity on all participants. The reduction or absence of light touch sensation to monofilament will be defined as < 8 of 10 applications detected in either foot.

Diabetic retinopathy will be measured by self-reported history of **laser treatment, diagnosis of retinopathy, and cataract extraction**. This information has been collected every 6 months since the beginning of LA and will continue in LA-E. The distribution of time to first occurrence of laser treatment on the back of the eyes will be compared between ILI and DSE using survival analyses described for total mortality.

Subgroup analyses: Pre-specified subgroup comparisons include sex, history of cardiovascular disease, race/ethnicity, and age. We will report tests of interactions to assess the consistency of differences between intervention groups for each of these subgroups.

Power: We project 80% conditional power to detect a 18% reduction in the rate of ILI participants experiencing ESRD compared to DSE ($\alpha=0.05$, two-sided log rank tests). These conditional power calculations use a boundary value of 2.1: this allows for a moderate

number of interim analyses during the LA-E, should the DSMB require this. If no interim monitoring is required, that boundary level is 1.96 and the power is slightly greater.

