Another aspect of quality of health is **late life depression** assessed by **Patient Health Questionnaire-9 (PHQ-9)**. PHQ-9 is a nine-item questionnaire with each item scored from 0 to 3. The sum of the nine items will provide a 0 to 27 severity score, with ≥ 10 indicating clinically significant depression. PHQ-9 was collected in LA-C and we will have two additional measurements from LA-E. Both the overall score and the prevalence of PHQ-9 ≥ 10 will be compared between DSE and ILI. In LA-E we propose to include several additional questionnaires that relate to aspects of quality of life that are of particular relevance to aging adults, namely loneliness, social isolation, resilience, and fatigability. Loneliness will be assessed by the **Three-Item Loneliness Scale** and the 20-item **Revised UCLA Loneliness Scale**. Each item in the Three-Item Loneliness Scale is scored from 1 to 3 [Hughes, 2004]. The summary score will range from 3 to 9, with higher score indicating higher level of loneliness. Each item in the Revised UCLA Loneliness Scale ranges from 1 to 4. Appropriate items will be reverse coded while computing the total score. Resilience will be assessed by a 6-item **Brief Resilience Scale (BRS)**. Responses vary from 1-5 for all six items. The final score will be calculated by dividing the total sum by the total number of questions answered. The 10-item **Pittsburgh Fatigability Scale for Older Adults** captures activities that span sedentary to high intensity of particular relevance to older adults [Glynn, 2015]. Linear mixed effects models will be applied to the scores from these questionnaires. In addition to comparing the overall mean scores between DSE and ILI on these measures, we will also examine the distribution of these scores and identify appropriate categorizations in the situation that the scores are highly skewed.

Subgroup analyses: Pre-specified subgroup comparisons include sex, history of cardiovascular disease, race/ethnicity, and age. We will report tests of interactions to assess the consistency of differences between intervention groups for each of these subgroups.

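### The 0-15 MNSI questionnaire score is analysed only as 4 or more versus less; a full-scale model should be pre-specified beside it, as the SAP already does for the MNSI exam score and the PHQ-9

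*Combined protocol and SAP*

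**What the plan says.** In SAP section 5.4 (Specific Aim 4), the MNSI questionnaire is scored as a sum of fifteen items, to be computed "and range from 0 to 15. The score will be dichotomized with" values of 4 or more counted as abnormal, with one reference for the cut. The binary variable "will be analyzed using logistic regression models appropriate for repeated binary outcomes", by GEE with a logit link. The covariates start with baseline status on the same cut ("The basic model will include baseline presence of" a score of 4 or more), followed by arm, time, arm-by-time and clinic. No analysis of the score itself is named.

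This is a long series: "MNSI questionnaire was administered in LA annually and in LA-C and will be collected at the two clinical visits in LA-E".

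Three neighbouring outcomes are handled both ways:

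- **MNSI exam score (0-8), section 5.4.** For the score, "We will use linear mixed effects models to test the intervention effect". For the cut, "We will also assess the intervention effect on prevalence of MNSI exam score of" 2.5 or more.
- **PHQ-9, section 5.5.** "Both the overall score and the prevalence of PHQ-9" at 10 or more will be compared between arms.
- **Renal function, section 5.4.** Creatinine thresholds are analysed as events, and eGFR by a mixed model.

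The questionnaire's rank is clear: "Supporting analyses include other measures of diabetic nephropathy and neuropathy". The principal outcome of Aim 4 is end-stage renal disease.

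**The concern.** Cutting a 16-level score at one point discards movement that stays on one side of it: a fall from 9 to 6, or from 3 to 1, counts as no change. The same happens to the baseline covariate, which then explains less of the later variation. The neuropathy measure with the most repeats (the exam score has at most three) therefore gets only a binary analysis, while the shorter exam series gets both.

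What is at stake is a supporting statement about neuropathy. If the intervention moves scores modestly across the scale, the binary result could look null when the score would have shown a difference. A score model added only after a null binary result would be post hoc, so it matters whether the plan names it in advance.

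**Working it through.** **No stated figure to reproduce.** Neither document gives power, effect size, SD or prevalence for the MNSI questionnaire. The only power statement in section 5.4 concerns end-stage renal disease. The 80% below is a hypothetical starting point at two-sided 0.05, so z = 1.960 + 0.842 = 2.802. The same quantiles reproduce the SAP's cost figure in section 5.2: 196 × 2.802 = $549 per year.

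**Assumed inputs:** the shape of the score, the share p scoring 4 or more, the type of effect, the number of visits and their correlation.

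**1. Whole-scale shift, one visit, normal score.** Relative efficiency of the cut against the mean is ARE = φ(c)² / [p(1 − p)], where c is the cut in SD units from the mean. Power with the cut is Φ(2.802 × √ARE − 1.960).

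| p at 4 or more | ARE | Power with cut |
|---|---|---|
| 10% | 0.342 | 37% |
| 20% | 0.280² / 0.16 = 0.490 | 50% |
| 30% | 0.576 | 57% |
| 50% | 0.399² / 0.25 = 0.637 | 61% |

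**2. Whole-scale shift, one visit, skewed score.** Negative-binomial scores truncated to 0-15, with an 8% lower mean in ILI and n set for 80% power on the mean:

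| Mean, size | p at 4 or more | Power with cut |
|---|---|---|
| 2, 1 | 20% | 63.1% |
| 2.5, 1.5 | 26% | 63.0% |
| 3, 2 | 34% | 62.6% |
| 3.5, 3 | 42% | 61.6% |

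For p of 20-50%, steps 1 and 2 together give about 50-63%.

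**3. Whole-scale shift, repeated measures with baseline adjustment.** Take k post-baseline visits with exchangeable correlation r on the score scale and r_b after the cut, and baseline on the same scale as the outcome. Write v = (1 + (k − 1)r)/k, and v_b likewise with r_b. Then ARE = ARE(one visit) × (v − r²)/(v_b − r_b²).

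Example: k = 10, r = 0.5, p = 30%, which gives r_b = 0.318.

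- v − r² = 0.550 − 0.250 = 0.300
- v_b − r_b² = 0.386 − 0.101 = 0.285
- ARE = 0.576 × 0.300/0.285 = 0.606, so power is 59%.

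Over k = 10-13, r = 0.4-0.7 and p = 10-50%, power runs from about 31% to 67%. Without baseline adjustment it is about 54-75%.

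**4. ILI prevents cases instead.** Let scores be a mixture of non-cases and cases (Poisson, truncated to 0-15), with ILI cutting the share of cases by 10% and leaving scores within each group unchanged. Example: means 1.5 and 6, with 25% cases in DSE and 22.5% in ILI.

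- Mean difference = 0.025 × (6 − 1.5) = 0.1125. The SD is about 2.50, so the standardised difference is 0.045.
- Share at 4 or more: 0.066 in non-cases and 0.849 in cases, so the difference is 0.025 × 0.783 = 0.0196. With p about 0.25, the SD is √(0.25 × 0.75) = 0.43, so the standardised difference is again 0.045.

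The cut therefore keeps the full 80%. With non-case means of 1-2, case means of 5-7 and 20-35% cases, most settings fall at about 73-84%, with edges near 70% and 85%. The loss is at most about ten points, and in some settings the cut does better.

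**The case against.** The strongest reply is that the power loss belongs to an assumed type of effect and not to this plan. A uniform shift favours the mean by construction. If the intervention works mainly by preventing neuropathy, the cut captures nearly all of the signal, as step 4 shows. This stands, and the documents do not say which kind of effect is expected.

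It can also be said that the cut is pre-specified and referenced, that the prevalence of a positive screen is easier to interpret than a mean on a symptom checklist, and that the data go back to the start of the trial. These points support keeping the binary analysis as planned. They do not explain why the score is left out here and kept for the exam score and the PHQ-9.

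A reader might infer that the cut is invalid because the title of the cited study places it in type 1 diabetes while this cohort has type 2. A title alone does not show that, and the absence of a guideline citation is not an error. A reader might also conclude that the score should replace the cut as the lead comparison. The SAP's own practice supports having both and does not say which should lead.

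Finally, section 4.3 plans mixed models for repeated continuous outcomes in general, and section 5.7 allows further modelling of trajectories. Neither names this score, and section 5.4 specifically defines the questionnaire outcome as binary.

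**Conclusion.** The point holds as a modest gap: the questionnaire score has no pre-specified full-scale analysis, its baseline value is also cut, and this departs without explanation from how the SAP treats comparable scores.

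The size is conditional. From a hypothetical 80%, a whole-scale shift leaves about 50-63% at one visit if 20-50% score 4 or more, and less if fewer do. It leaves roughly 31-67% with repeated measures and baseline adjustment. Prevention of cases leaves most or all of the 80%. Every figure depends on the assumed distribution, correlation and effect type.

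It would be tempting to state that this comparison falls from 80% to 50-63% power, or that a true effect will probably be reported as null. The documents support neither: they claim no power for the MNSI, and the answer changes with the type of effect. Nor is Aim 4 at risk, since its hypothesis concerns end-stage renal disease, and neuropathy is also assessed by the exam score, its cut and the monofilament test. This is a worthwhile improvement and not a flaw in the main inference.

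**What to change.** In SAP section 5.4, pre-specify a linear mixed model of the 0-15 questionnaire score alongside the planned GEE analysis. Include baseline score, clinic, time, arm and arm-by-time, and use robust standard errors because the score is likely to be skewed. This follows the exam-score model with the baseline score added; that score is available, since the planned binary model already uses a variable derived from it. Keep the odds ratio for 4 or more exactly as planned.

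The cost is a few lines of SAP text and one model on data already scheduled for collection. The downside is one more supporting test in a plan that, by section 4.1, does not control type 1 error across outcomes. Both results should therefore be reported together, whichever way they fall.

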Annual collection of the self-reported number of **falls** was initiated at year 8 of LA and continued in LA-C. In combination with the additional data collected every 6 months in LA-E, we will compare the average proportion of participants who reported at least one fall over time between DSE and ILI since year 8. The basic model will include an indicator variable for intervention assignment, follow-up time, and the interaction between the intervention and follow-up time while adjusting for clinic centers. The model will use generalized estimating equations (GEE), a logit link, a binomial variance, and include compound symmetry covariance to account for the correlations among repeated measures. A contrast, incorporating a robust variance estimate to account for potentially mis-specified covariance, will be used to test for the significance of the overall intervention effect across follow-up. In supporting analyses, we will also use the total number of falls reported as a dependent variable in negative binomial regression models. The basic model will include an indicator variable for intervention assignment, clinic centers as covariates, and the log follow-up time as an offset. Robust standard errors will be used for hypothesis testing. The average number of falls will be estimated for DSE and ILI. We will also examine the CI for the dispersion parameter. If there is evidence that a dispersion parameter is not necessary, we will resort to a Poisson regression model.

In addition to actual falls, a self-reported concern about falling will be assessed using a 16-item **Fall Self-Efficacy Scale International (FES-I)** at the two clinic visits in LA-E. Each item ranges from 1 to 4, representing 'not at all concerned' to 'very concerned' [Yardley, 2005]. The total FES-I score will be compared between DSE and ILI using linear mixed effects models. The basic model will include an indicator variable for intervention assignment, follow-up time, and the interaction between the intervention and follow-up time while adjusting for clinic centers. The covariance between repeated measures will be characterized with an unstructured covariance structure and a contrast will be used to test for the significance of the overall intervention effect across follow-up.

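### SAP 5.4 tests the repeated MNSI ≥ 4 outcome with a likelihood ratio test, which the GEE model it specifies does not have; a robust contrast should replace it

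*Combined protocol and SAP*

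**What the plan says.** SAP Section 5.4 (Specific Aim 4, supporting analyses) dichotomises the MNSI questionnaire score at 4 and analyses it "using logistic regression models appropriate for repeated binary outcomes". The data are longitudinal: "MNSI questionnaire was administered in LA annually and in LA-C and will be collected at the two clinical visits in LA-E", and "All data collected since randomization will be included".

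The method is explicit: "The model will use GEE, a logit link, and a binomial variance". For the dependence between visits, "we will use an exchangeable correlation matrix and a robust covariance estimate". Besides baseline MNSI status, the model contains "an indicator variable for intervention assignment, follow-up time, and the interaction between the intervention and follow-up time while adjusting for clinic centers".

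The test is then stated without qualification: "Significance for the intervention effect will be based on the likelihood ratio test". The odds ratio and its 95% interval come from the fitted model, and differences at single visits are tested by linear contrasts.

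Two other places bear on this:

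- The same sentence about the likelihood ratio test appears in Protocol Section 1.5 and SAP Section 5.1, where it follows proportional hazards regression for mortality.
- SAP Section 5.3 fits a GEE logit model to repeated falls data and tests it differently: "A contrast, incorporating a robust variance estimate to account for potentially mis-specified covariance, will be used to test".

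**The concern.** A likelihood ratio test compares the maximised likelihoods of two nested models. GEE solves estimating equations for the marginal mean. Its working correlation is a device for weighting and does not define a joint distribution of a person's repeated binary responses. There is therefore no likelihood for the exchangeable fit and no ordinary likelihood ratio statistic.

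An analyst who wants to follow the sentence will most readily find the binomial log-likelihood from a logistic model that counts every visit as an independent observation. Intervention assignment does not vary within a person, so positive within-person correlation makes that likelihood overstate the information about the arm effect, and the test rejects too often.

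At stake is the p-value for the intervention effect on questionnaire-defined neuropathy. It could contradict the robust confidence interval reported beside it, or it would have to be replaced by a test chosen after the data are in hand.

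**Working it through.** **Consistency.** The plan gives no power, sample size or alpha for the MNSI analysis, so it has no figure to reproduce. Set side by side:

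| Place | Model | Stated test | Do they match? |
|---|---|---|---|
| SAP 5.1, Protocol 1.5 (mortality) | Proportional hazards regression | Likelihood ratio | Yes; the partial likelihood supports it |
| SAP 5.3 (falls) | GEE, logit | Contrast with robust variance | Yes |
| SAP 5.4 (MNSI ≥ 4) | GEE, logit, exchangeable, robust covariance | Likelihood ratio | No |

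**Inputs for the size of the effect.**

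- Two-sided alpha 0.05: assumed, as in the Aim 4 power paragraph.
- Post-baseline measurements per person, m: the SAP gives a schedule but no count. Assumed 8 to 13.
- Residual within-person correlation, ρ: not in the documents. Assumed 0.05 to 0.6.

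**Design-effect approximation.** For a 1-df test of an arm effect averaged over visits, the independence likelihood understates the variance by a factor D = 1 + (m − 1)ρ. The actual type I error is then 2 × [1 − Φ(1.96/√D)].

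- Low end, m = 8 and ρ = 0.05: D = 1 + 7 × 0.05 = 1.35; 1.96/√1.35 = 1.69; type I error 9.2%.
- High end, m = 13 and ρ = 0.6: D = 1 + 12 × 0.6 = 8.2; 1.96/√8.2 = 0.68; type I error 49.4%.

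| ρ | D, m = 8 | Type I error | D, m = 13 | Type I error |
|---|---|---|---|---|
| 0.05 | 1.35 | 9.2% | 1.6 | 12.1% |
| 0.1 | 1.7 | 13.3% | 2.2 | 18.6% |
| 0.2 | 2.4 | 20.6% | 3.4 | 28.8% |
| 0.3 | 3.1 | 26.6% | 4.6 | 36.1% |
| 0.4 | 3.8 | 31.5% | 5.8 | 41.6% |
| 0.5 | 4.5 | 35.6% | 7.0 | 45.9% |
| 0.6 | 5.2 | 39.0% | 8.2 | 49.4% |

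**Simulation under the null.** The approximation leaves out the baseline covariate and the interaction. A simulation therefore used a random-intercept logistic model with 1,000 participants, 13 visits and 400 replicates per setting. The fitted terms were the SAP's except clinic: baseline status, time, arm and arm by time. Time was centred, so the arm coefficient is the effect at mid-follow-up.

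| Fitted residual correlation | Independence LRT, 1 df (arm) | Independence LRT, 2 df (arm and interaction) | GEE robust Wald, 1 df | GEE robust Wald, 2 df |
|---|---|---|---|---|
| 0.13 | 23% | 18% | 5.5% | 5.3% |
| 0.27 | 35% | 28% | 4.8% | 5.5% |

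The Monte Carlo standard error near 5% is √(0.05 × 0.95/400) = 1.1 percentage points, so the robust tests are consistent with the nominal level.

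**Cross-check.** Putting the fitted residual correlations into the formula with m = 13 gives D = 1 + 12 × 0.135 = 2.62 and a type I error of about 23%, and D = 1 + 12 × 0.274 = 4.29 and about 34%. These agree with the 1-df simulation results. The approximation is adequate provided ρ is read as the correlation left after baseline adjustment. The 2-df test is less inflated because its interaction component is a within-person comparison.

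**The case against.** The strongest defence is that nobody would run the independence test. To do so the analyst must set aside the exchangeable correlation and robust covariance that the same paragraph prescribes. The odds ratio and interval come from the robust fit, so a conflicting p-value would be visible beside them. The sentence also matches the mortality text, where it is correct, which suggests carried-over wording, though that is an inference. Much of this stands: the documents do not show an intention to ignore clustering. It does not rescue the sentence, because the stated test still has to be replaced and the plan does not say by what.

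Three stronger readings are tempting, and the documents do not support them.

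- *That no likelihood-ratio-type test is possible, so an independence test is the only option.* Working quasi-likelihood ratio statistics with a corrected reference distribution exist. The objection is to the ordinary, unqualified test, which is the one the SAP names.
- *That the type I error can be pinned to a narrow band.* Taking 12 to 14 visits and correlations of 0.2 to 0.5 gives 27% to 47%, but neither input is in the documents and these are not bounds. Adjustment for baseline status lowers the relevant correlation, and a joint test with the interaction is less inflated. Participants will also differ in visit count: about 3,800 of the 5,145 randomized are expected in the Extension, so 1,345/5,145 = 26% would contribute no Extension visits.
- *That the neuropathy findings, or Aim 4, are compromised.* The principal Aim 4 outcome is ESRD, analysed by survival methods. SAP Section 4.1 gives secondary endpoints a supportive role and does not control type I error across all outcomes. No power figure or monitoring rule uses this p-value.

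**Conclusion.** The rule is wrong as written: the named test does not belong to the named model, and the SAP's own falls analysis shows the appropriate one. If the ordinary independence likelihood were used, a nominal 5% test would reject a true null about 9% to 49% of the time by the design-effect approximation (8 to 13 visits, residual correlation 0.05 to 0.6). In the baseline-adjusted simulations the figure was 18% to 35% (13 visits, residual correlation 0.13 to 0.27). Visit count and correlation are assumptions throughout; the inflation appears at every value examined, but its exact size is not known.

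The consequence is confined to one p-value in a supporting analysis of a secondary aim. The robust GEE odds ratio, confidence interval and visit-level contrasts stand. It should be corrected, but it threatens no primary or secondary conclusion.

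**What to change.** Replace the sentence in the MNSI questionnaire paragraph of SAP Section 5.4 with:

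> Significance of the overall intervention effect across follow-up will be based on a robust-variance Wald (or generalized score) contrast from the GEE model.

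This brings the analysis into line with falls in SAP Section 5.3. It also settles a second ambiguity: with an intervention-by-time term in the model, the intervention effect could mean the main-effect coefficient, a joint test with the interaction, or the average over follow-up. The new wording makes it the average. One of the two tests, Wald or generalized score, should be chosen before analysis.

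The same sentence can cover the GEE analysis of MNSI exam score ≥ 2.5 later in Section 5.4, which names no test. If a likelihood ratio test is wanted for its own sake, the model would have to become a random-effects logistic regression, which changes the odds ratio from marginal to participant-specific.

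The cost is one sentence of SAP text. Data collection, sample size, power and, under the recommended wording, the GEE odds ratio are unchanged.
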